3. STUDY POPULATION

The study population is all patients aged ≥ 16 years of age who have been referred by the multi-disciplinary team (MDT) for lung resection for known or suspected lung cancer. Eligibility criteria are as inclusive as possible to promote the applicability of the evidence obtained during the trial. For specific inclusion/exclusion criteria see **Figure F1**.

Recruitment over time against targets will be presented overall (**Figure F2**).

The planned sample size for the VIOLET study is 498 patients. This sample size would be sufficient to detect a difference of 0.25 standard deviations in physical function between the VATS and open groups with 90% power and 5% significance (2-tailed). The total sample size will allow for a 20% dropout at one year.

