- **Time to event outcomes** will be summarised by the median and IQR or mean and SD in each treatment group, estimated from survival modelling. Outcomes will be compared using Cox’s proportional hazards, parametric models, or interval censoring methods for analysing discrete time data, as appropriate. The choice of model used will depend on the outcome event and the distribution of the data. Treatment comparisons will be presented as hazard ratios (HRs) and 95% CI if a proportional hazards model is used, time ratios (TRs) and 95% CI if an accelerated failure time model is used, or OR and 95% CI if a discrete time proportional odds model is used. Times will be censored using censoring variables defined below:

Outcome	Censor variable
Time from surgery to hospital discharge	Date of death, if patient died before hospital discharge
Time to uptake of adjuvant treatment	Last visit date, if patient did not receive any adjuvant treatment
Overall survival	Last visit date, if patient was alive at the end of the study follow-up
Disease free survival	Last visit date, if patient was disease free at the end of the study follow-up

- **Continuous longitudinal outcomes** will be summarised as means and SDs (or medians and IQRs if distributions are skewed) at each time point. Outcomes will be compared using linear mixed effects methodology with the treatment group and study design variables fitted as per section 5.2.1, and patient terms fitted as random effects. Separate parameter estimates will be incorporated into models for 1) the mean baseline response across both treatment groups and 2) at each post-intervention time point for each treatment (i.e. saturated model with time fitted as a categorical variable). If the time x treatment interaction (post-intervention) is not statistically significant at the 10% level an overall treatment effect will be reported. If the interaction is statistically significant the changes in treatment effect with time will be described. Deaths will be accounted for by modelling HRQoL and survival jointly. When modelling EQ5D, patients who have died will be assigned a score of 0 for all future time points. Different variance/covariance structures will be explored, and the structure that provides the best fit in terms of information criteria such as AIC, BIC and likelihood ratio tests will be used. Treatment comparisons will be presented as adjusted differences in means with 95% CI.

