6.2.8 Missing data

In all tables missing data for continuous variables will be indicated by footnotes. For category variables missing data will be highlighted by use of observation counts. If the amount of missing data differs substantially between treatment groups potential reasons will be explored.

Missing predictors:

There will be no missing data for any of the randomisation factors (by design). All other potential predictors are baseline measurements of continuous longitudinal outcomes, and due to the joint modelling approach described previously the handling of missing values for such data is considered in the context of missing longitudinal data (see below).

Missing outcomes measured at one time point:

- If the proportion of missing data is less than 5% then complete case analysis will be performed (i.e. excluding cases with missing data).
- If the proportion of missing data is above 5% multiple imputation methods will be considered. A general imputation model that uses an iterative procedure to generate imputed values will be used to generate multiple complete data sets (e.g. using Stata's `mi impute`). The model of interest will be fitted to each of the complete data sets and effect estimates combined using Rubin's rules. If appropriate, methods such as predictive mean matching will be used in order to ensure that imputed values lie within specific ranges.

Missing longitudinal data:

- For continuous data measured at multiple time points preoperative values will be modelled jointly with those measured postoperatively, as described previously, thereby allowing all cases with at least one observation to be included. If the proportion of cases that do not have at least one observation is above 5% then multiple imputation methods will be considered (see above). If appropriate (the level of missingness is >20%) then any variables that are predictive of missingness will be identified, and if there is reason to suggest that an assumption of missing at random (MAR) given these variables is reasonable (especially likely if the variable was measured pre-operatively) then such variables will be adjusted for in the models of interest. These models can be shown to provide unbiased estimates of the treatment effect and moreover multiple imputation approaches would not be expected to recover any additional information.

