APPENDIX A: SKELETON TABLES AND FIGURES

The following summarises the planned outputs:

Section	Outputs
Section 1 Population	Tables, figures and listings detailing the study population Figure F1 Flow of participants Figure F2 Predicted and actual recruitment Table T1 Protocol deviations Table T2 Details of conversions from VATS to open surgery Table T3 Withdrawals
Section 2 Baseline and intra-operative data	Summary tables of demographic and operative information Table T4 Baseline demographic and clinical characteristics Table T5 Operative details
Section 3 Additional descriptive information	Summary tables of additional descriptive information Figure F3 Pathology flow chart Table T6 Patient blinding at 2 days post-surgery Table T7 Patient blinding at discharge Table T8 Nurse blinding at discharge Table T9 Nurse blinding at 5 weeks Table T10 Nurse blinding at 12 months
Section 4 Primary and secondary outcome data	Summary data and treatment estimates for primary and secondary outcomes Table T11 Primary outcome Figure F4 Primary outcome Table T12 In-hospital secondary outcomes Table T13 Additional secondary outcomes Table T14 Pain scores in the first two days post-surgery Figure F5 In-hospital secondary outcomes Figure F6 Mean ratios of in-hospital analgesia Figure F7 Additional secondary outcomes Table T15 QLQ-C30 global health status/functional scale scores Figure F8 Global health status over time Table T16 QLQ-C30 symptoms scale scores Table T17 QLQ-LC13 Table T18 EQ5D Table T19 Adverse events and serious adverse events in-hospital Table T20 Serious adverse events during follow-up Table T21 Sensitivity analysis of primary outcome excluding patients with benign disease Figure F9 Adverse events in-hospital Figure F10 Subgroup analysis of pain score Figure F11 Sensitivity analysis of survival outcomes adjusting for pathological disease stage Figure F12 Exploratory analysis of in-hospital pain score by of thoracotomy performed Figure F13 Exploratory analysis of QLQ-C30 pain score by type of thoracotomy performed Table T22 Pain scores by number of port sites Table T23 Exploratory analysis comparing pain scores by number of port sites Table T24 Exploratory analysis comparing length of stay by number of port sites

Figure F1 Flow of participants

Notes:

¹ Patients may be ineligible for more than one reason

Benign patients are only followed-up to 5 weeks post-randomisation; allocated to open (n=xx), allocated to VATS (n=xx)

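### EQ5D: zeros for known deaths and survivors' incomplete scores share one missing-at-random model, which over-weights death and can bias the comparison modestly

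*SAP*

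**What the plan says.** SAP section 6.2.2 classes EQ5D as a longitudinal HRQoL outcome. It is analysed by a linear mixed model with a common baseline mean and a separate mean for each arm at each later visit ("saturated model with time fitted as a categorical variable"). Two sentences deal with death. The first covers HRQoL generally: "Deaths will be accounted for by modelling HRQoL and survival jointly". The second is specific: "When modelling EQ5D, patients who have died will be assigned a score of 0 for all future time points". The SAP does not say whether the zeros replace the joint model for EQ5D or are added to it.

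Section 6.2.8 treats missing longitudinal values by modelling all available data, "thereby allowing all cases with at least one observation to be included". Its further steps are limited:

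- "If the proportion of cases that do not have at least one observation is above 5% then multiple imputation methods will be considered".
- Above 20% missingness, predictors of missingness may be added to the model.
- For unequal missingness between arms, "If the amount of missing data differs substantially between treatment groups potential reasons will be explored", with no analysis named.

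None of these steps uses the fact that a non-responder is alive.

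Missing survivor forms are to be expected. Section 3 says "The total sample size will allow for a 20% dropout at one year", and the note to Figure F1 in Appendix A says "Benign patients are only followed-up to 5 weeks post-randomisation".

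**The concern.** Once death is scored 0, being dead or alive is part of the outcome. A known death always supplies a score, whereas a survivor supplies one only if the form is returned. Whether a visit is missing therefore depends on the value at that visit. Missing at random fails even if survivors skip forms purely by chance. The model implicitly predicts a living non-responder from an arm distribution that includes the dead.

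Two consequences follow for the differences in Table T18:

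- An arm that retains fewer survivors looks worse, even when mortality and survivors' quality of life are the same in both arms.
- A real mortality difference is exaggerated when forms are missing, even if equally often in both arms.

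**Working it through.** The SAP gives no EQ5D figure to reproduce, and no mortality, EQ5D mean, SD or retention by arm. Those inputs below are assumptions. From the SAP come the zero for death, the saturated model, the six time points (baseline, 2 and 5 weeks, 3, 6 and 12 months) and the overall 20% dropout allowance.

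**Step 1: weight given to death.** Let p be the proportion dead, all known, and r the proportion of survivors observed. The dead make up p / [p + (1 − p)r] of the observed scores.

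- p = 0.10, r = 0.80: 0.10 / (0.10 + 0.72) = 12.2%, against a true 10%.
- p = 0.05, r = 0.80: 0.05 / (0.05 + 0.76) = 6.2%, against a true 5%.

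**Step 2: observed mean.** With survivor mean m, the true mean is (1 − p)m and the observed mean is (1 − p)rm / [(1 − p)r + p]. Take p = 0.08 in both arms and m = 0.80, so the true mean is 0.736.

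- 10% v 30% missing: 0.6624/0.908 = 0.7295 and 0.5152/0.724 = 0.7116, a spurious difference of 0.018.
- 15% v 25% missing: 0.6256/0.862 = 0.7258 and 0.552/0.77 = 0.7169, a spurious difference of 0.009.
- 20% v 20% missing: 0.5888/0.816 = 0.7216 in both arms. Both are too low, but there is no difference.

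These are raw means. The mixed model recovers part of the error from a survivor's earlier scores.

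**Step 3: the mixed model, 8% mortality in both arms, no true difference.** Several simulations under differing assumptions gave these spurious 12-month differences, in favour of the better-retained arm:

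- 10% v 30% missing: 0.007 to 0.014.
- 10% v 25% missing: about 0.010.
- 15% v 25% missing: 0.003 to 0.007.

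With 249 per arm, 0.010 to 0.014 is about 0.4 to 0.5 of a standard error. Averaged over the follow-up visits, one set of runs gave 0.006 (10% v 30%) and 0.003 (15% v 25%).

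**Step 4: dependence on mortality.** This is a maximum-likelihood fit with 150,000 per arm, survivor mean 0.80, SD 0.20, correlation 0.6 and dropout among survivors at random. Ranges run from unstructured to compound-symmetry covariance.

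| Mortality, both arms | 12 months, 15% v 25% missing | 12 months, 10% v 30% missing | Mean over visits, 10% v 30% missing |
|---|---|---|---|
| 3% | 0.003–0.004 | 0.006–0.007 | 0.002 |
| 5% | 0.005–0.006 | 0.010–0.011 | 0.003 |
| 10% | 0.009–0.010 | 0.016–0.020 | 0.005–0.006 |
| 15% | 0.011–0.014 | 0.022–0.027 | 0.007–0.008 |

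In 400 simulated trials of 249 per arm at 10% mortality, the nominal 5% test at 12 months rejected in 3.8% (20% v 20% missing), 7.0% (15% v 25%) and 11.0% (10% v 30%). At 5% mortality with 10% v 30% it rejected in 7.5%.

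**Step 5: real mortality difference, 20% missing in both arms.** At 5% v 10% mortality the model gives 0.046 against a true 0.040. In a second set-up (SD 0.22, correlation 0.5), 6% v 10% gives 0.040 against 0.035, and 4% v 12% gives 0.069 against 0.060. The exaggeration is about 15%.

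**Step 6: when deaths are lost too.** If deaths after loss to follow-up are as unseen as the forms, 10% mortality with 10% v 30% lost gives a difference of only 0.0004.

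None of these fits included the centre and surgeon random effects or a survival submodel.

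**The case against.** The strongest reply is that the bias is conditional and small. A reader might infer that a death is never missing under this plan, but the SAP does not say so. Only a known death can be scored 0, and tracing after loss is not described. Overall survival is censored at the last visit, and Table T3 has a row for withdrawal from follow-up. Step 6 shows that the bias all but disappears if deaths and forms are lost together. This point stands for patients lost altogether. It does not cover a patient still in follow-up who skips a questionnaire.

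The inputs are assumed, and the 20% in section 3 is an overall allowance with no split by arm. EQ5D is one secondary outcome on a scale from −0.59 to 1.00. Section 6.2.2 reports an overall effect unless the interaction is significant at the 10% level, which dilutes the 12-month figures. The 7.0% rejection rate has a 95% interval of about 4.7% to 10.0%, which is compatible with 5%. All of this stands and limits the weight of the point.

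A reader might also infer that the two sentences on death contradict each other. The text does not force that, since the EQ5D sentence can be read as a specific exception. That reading still leaves the zeros in the mixed model. If both rules apply, the joint model does not clearly remove the problem while the zeros remain in the longitudinal data.

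Nor do the documents support reading the score of 0 as the mistake. The fault lies in mixing scores that are always present with scores that may be missing. The benign patients' planned stop at 5 weeks adds missing survivor scores but, being balanced by randomisation, should not by itself create a difference.

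**Conclusion.** The point holds as a modest weakness in the analysis of one secondary outcome. Where deaths are known and some survivors' forms are missing, the planned EQ5D model over-weights death, and no remedy in section 6.2.8 corrects this. At an assumed 8% mortality in both arms, the between-arm error at 12 months is roughly 0.003 to 0.014 for retention gaps of 10 to 20 percentage points, and smaller when averaged over visits. A real mortality difference is inflated by about 15% when 20% of forms are missing in both arms. With equal mortality and equal retention the comparison is unbiased, although both arm means are too low. The sizes rest on the assumed mortality, EQ5D distribution and retention. The mechanism follows from sections 6.2.2 and 6.2.8 alone, provided deaths are better ascertained than survivors' forms.

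**What to change.** Keep death at 0 and change the order of operations. Suggested wording for section 6.2.2:

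*Missing EQ5D scores of patients known to be alive at a visit will be multiply imputed, separately by arm, from an imputation model fitted to scores recorded while alive, using earlier and later scores. A score of 0 will then be inserted at each visit after death. The planned mixed model will be fitted to each completed data set and the results combined by Rubin's rules. For EQ5D this replaces joint modelling with survival.*

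The SAP should also say how vital status at each visit is established and how patients of unknown status are handled.

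Section 6.2.8 argues that imputation would add no information to the longitudinal models. Here it does, because it uses the fact that the patient is alive. In the scenarios checked, including death depending on the previous score, this procedure cut the error to about 0.001 or less.

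A tempting alternative is to model living patients' scores and multiply the model mean by the survival probability. It should not be used. A likelihood fit to those scores extrapolates past death, so it does not estimate the mean among the living when death depends on earlier EQ5D. It removes the retention artefact when death is unrelated to earlier scores. With log-hazard rising 1.2 per SD lower previous score, about 6% v 10% mortality and 20% missing in both arms, the true difference was 0.0245. The planned model and the product both gave 0.0285.

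The cost is a SAP amendment and some imputation work, with tools section 6.2.8 already provides for. Table T18 would use pooled tests in place of the direct likelihood ratio test preferred in section 6.2.3.

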6.2.3 Statistical significance

For hypothesis tests two-tailed p-values < 0.05 are considered statistically significant. Likelihood ratio tests will be used in preference to Wald tests for hypothesis testing.

6.2.4 Model assumptions

For all methods outlined underlying assumptions will be checked using standard methods, e.g. residual plots, tests for proportional hazards, etc. If assumptions are not valid then alternative methods of analysis will be sought. If outlying observations are found which mean models do not fit the data adequately, such observations will be excluded from the main analyses and comments made in footnotes. Sensitivity analyses may be performed to examine the effect on the study's conclusions of excluding outlying observations.

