3.5 Analysis population

The analysis population consists of all randomised patients excluding:

- Patients who died after randomisation but prior to any data collection.

- Patients withdrawn who were unwilling for data collected to be used.

The main study analyses will be performed on an ITT basis, including randomised participants who are not found to have lung cancer. A modified ITT analysis excluding these participants will also be performed for the primary outcome.

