6.2.2 Analysis models

All outcomes listed in the study protocol will be presented as per the template tables **Table T11 to T18**. General methods of presentation and assessing treatment effects are outlined below. For all treatment comparisons, the open lobectomy group will be the reference group. Details specific to each outcome are described as appropriate.

Each outcome will be considered under a certain data type, as outlined in the table below:

Date type	Outcomes
Binary	Proportion of patients receiving adjuvant treatment Proportion of patients who undergo complete resection during the procedure Proportion of patients who experience prolonged incision pain Any in-hospital adverse event Any in-hospital serious adverse event
Categorical	Proportion upstaged to pN1 disease after the procedure Proportion upstaged to pN2 disease after the procedure
Time to event	Time from surgery to hospital discharge Time to uptake of adjuvant treatment Overall survival Disease-free survival
Longitudinal	Physical function (primary) Pain scores in the first two days post-surgery HRQoL (QLQ-C30, QLQ-LC13, EQ5D)

Each type of data will be summarised and compared between the groups according to the following:

- **Binary outcomes** will be presented as numbers and percentages of patients in each treatment group. Outcomes will be compared between treatment groups using generalised linear models, with treatment comparison estimates presented as adjusted risk ratios (RR) and risk differences (RD) with 95% confidence intervals (95% CI). Formal statistical comparisons of treatment effects will only be performed if more than ten patients in total experience the outcome (with at least one event in each treatment group).
- **Categorical outcomes** will be presented as numbers and percentages of patients in each treatment group in each category. Outcomes will be compared between treatment groups using multinomial logistic regression, with treatment comparison estimates presented as adjusted RR and 95% CI.

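### SAP section 6.2.4 makes deletion of outlying observations part of the main analyses, primary outcome included, with no threshold, no masked decision and only an optional check

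*SAP*

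**What the plan says.** SAP section 6.2.4 opens with "For all methods outlined underlying assumptions will be checked using standard methods" and adds that other methods will be looked for if assumptions fail. It then treats outliers separately: "If outlying observations are found which mean models do not fit the data adequately", then "such observations will be excluded from the main analyses and comments made in footnotes". The section ends: "Sensitivity analyses may be performed to examine the effect on the study's conclusions of excluding outlying observations".

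Section 3.5 states: "The main study analyses will be performed on an ITT basis". On who is analysed it says "The analysis population consists of all randomised patients excluding" two groups: those who died after randomisation before any data were collected, and those who withdrew and did not want their data used. Outlying values are not mentioned.

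Section 6.2.2 places physical function, the primary outcome, among the longitudinal outcomes analysed by a linear mixed model. Section 6.2.6 commits to one sensitivity analysis of the primary outcome, which leaves out patients with benign disease. The output list in Appendix A contains no analysis with and without outliers.

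**The concern.** The usual order is reversed. Deletion belongs to the main analysis, and looking at its effect is left to discretion. The choice of which values count as outlying is made after a model has been fitted to the data, and nothing says that whoever makes it is masked to allocation. Nor does a value have to be wrong to be removed.

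Physical function at 5 weeks is what the trial sets out to compare. A very low score may be a recording error or may be a genuinely poor recovery, and the rule does not distinguish the two. If genuine low scores are more common after one operation, deleting them removes part of the difference being estimated. Trimming the tails also shrinks the residual variance, so the confidence interval can be too narrow even when the arms do not differ. With no threshold fixed, the primary estimate can depend on a choice made after the data are seen.

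**Working it through.** The SAP gives no figure to reproduce here: no outlier definition, no expected count and no SD for physical function. The check is therefore a comparison of the text, followed by two illustrations on assumed inputs.

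**Text**

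1. *Scope.* Section 6.2.4 applies to all methods outlined. Section 6.2.2 includes the primary mixed model among them, so the rule reaches the primary outcome.
2. *Force.* Exclusion is mandatory once fit is judged inadequate. The sensitivity analysis is permissive.
3. *Population.* Section 3.5 lists two exclusions from all randomised patients. Section 6.2.4 adds a further, data-dependent loss of outcome values that section 3.5 does not acknowledge.
4. *What is lost.* For the primary outcome it is an observation. Section 6.2.8 keeps every case with at least one observation, so the patient stays in the model through other visits, but the 5-week value itself is gone. For an outcome with a single value per patient, such as time to discharge, losing the observation removes the patient from that analysis.
5. *Missingness.* The longitudinal approach in section 6.2.8 relies on data being missing at random. A value deleted because of its own size is not missing at random.
6. *Guarantee.* Neither section 6.2.6 nor Appendix A commits to an analysis that retains all observations once the rule has been applied.

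**Illustration 1: simple 5-week means**

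| Input | Value | Source |
|---|---|---|
| Target difference | 0.25 SD | SAP section 3 |
| SD of physical function | 20 points | assumed |
| Outlier share, arm A | 1% | assumed |
| Outlier share, arm B | 3% to 5% | assumed |
| Gap below the mean of the remaining patients | 50 to 60 points | assumed |

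If a share p of an arm lies g points below the mean M of the rest, the arm mean is M - p x g with all data and M after deletion. The between-arm difference therefore shifts by (p_B - p_A) x g.

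- Low: (0.03 - 0.01) x 50 = 1.0 point
- High: (0.05 - 0.01) x 60 = 2.4 points
- Target: 0.25 x 20 = 5 points
- Ratio: 1.0/5 = 20% to 2.4/5 = 48%

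**Illustration 2: dependence on the cut-off**

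All inputs to this simulation are assumed, except that 199 per arm is 498 x 0.8 / 2. Scores are 100 x Beta(4, 1.4), with poor recoverers at 100 x Beta(1.2, 8), rounded to steps of 100/15. One arm has 5% poor recoverers and the other has more. Residuals beyond the cut-off are deleted once, arms are compared by a two-sample t-test, and there are 4,000 runs per row.

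| Extra poor recoverers | Cut-off | Difference, all data | Difference after deletion |
|---|---|---|---|
| 5 percentage points | 2 SD | 3.05 | 0.82 |
| 5 percentage points | 2.5 SD | 3.07 | 2.10 |
| 5 percentage points | 3 SD | 3.07 | 3.13 |
| 8 percentage points | 2 SD | 4.87 | 1.75 |
| 8 percentage points | 2.5 SD | 4.85 | 4.21 |
| 8 percentage points | 3 SD | 4.90 | 4.98 |

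With no true difference, the test rejected in 4.3-5.1% of runs on all data and in 7.2-8.9% after deletion. In a separate run, taking the smallest p-value among no deletion and the three cut-offs gave about 13%.

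**The case against.** The best defence is that the rule is narrower than it first appears. It acts only when outliers spoil the fit, other methods are to be sought when assumptions fail, Table T11 already allows a geometric mean ratio, and exclusions must be disclosed in footnotes. This has some force, but the sentence about alternative methods does not displace the one that prescribes exclusion, the order of the two steps is not stated, and a footnote does not restore the estimate.

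Several stronger readings are tempting but not supported:

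- A reader might infer that patients drop out of the ITT population for the primary outcome. They do not: the allocated arm and the other visits are kept. The conflict lies in discarding valid 5-week outcomes.
- A reader might assume that most outliers will be real poor recoveries. The SAP says nothing on this, and a score bounded at 0 and 100 limits how extreme a valid value can be. The rule is at fault because it does not ask.
- Length of stay looks like the natural example because of its long tail. If a Cox model is used, only the order of events matters and one very long stay has little leverage. The example is stronger under the parametric models that section 6.2.2 also allows.
- The 20-48% ratio could be taken as an expected bias. It rests on assumed inputs and a raw mean at one visit. In the mixed model, retained visits inform the 5-week estimate. If the interaction is not significant at 10%, an overall effect is reported, which dilutes a single deleted value.

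The simulation has the same limits. It deletes automatically and uses a t-test, so its rejection rates do not carry over to the planned analysis. At 3 SD it shows almost no change in the estimate.

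**Conclusion.** The point stands. Section 6.2.4 prescribes removal of outcome values from the main analyses, including the primary one, on a post-data judgement of fit, with no threshold, masking or error check, and no guaranteed analysis on all observations. That conflicts with the ITT commitment in section 3.5 and creates missing values that the planned model cannot assume to be missing at random. It can bias the treatment effect and understate its standard error.

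Neither the direction nor the size can be derived from the SAP. The 1.0-2.4 points against a 5-point target is an upper-end illustration. What the simulation adds is qualitative: under one set of assumptions, the same data gave anything from a largely erased difference to an unchanged one according to a cut-off that the SAP leaves open. Whether the rule is ever triggered depends on the data, and nothing here shows that the trial's conclusion would change.

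**What to change.** Reword section 6.2.4 so that:

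- all verified observations stay in the main ITT analysis;
- only values confirmed as data errors are corrected or removed, with that decision made blind to allocation;
- poor fit is handled by transformation, robust methods or bootstrap standard errors. Table T11 already foresees a geometric mean ratio, but a physical function score can be 0 (raw score 4 gives [1 - (4 - 1)/3] x 100 = 0), so any log scale needs a stated way of handling zeros;
- exclusion of outliers appears only as a sensitivity analysis, with the residual threshold fixed in advance and the number excluded reported by arm.

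Add that sensitivity analysis to section 6.2.6 and to the output list in Appendix A.

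The cost is an SAP amendment and slightly more analysis work. Confidence intervals may be wider than after deletion. Sample size and data collection are unaffected.
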